9.4.2.3. Vital Signs

Descriptive statistics for weight and postural vital signs (supine and standing systolic and diastolic BP and pulse rate), respiration rate, and temperature at baseline and changes from baseline at each assessment time point will be presented by study intervention group within each cohort.

Vital sign values will be considered PCS within the corresponding cohort if they meet both the observed-value criteria and the change-from-baseline-value criteria that will be detailed in the SAP. The number and percentage of participants who have PCS postbaseline vital sign values will be tabulated by study intervention within the double-blind Study Intervention Period and Postintervention Period separately for the corresponding cohort. The percentages will be calculated relative to the number of participants who have available non-PCS baseline values and at least 1 postbaseline assessment in the specific period for the corresponding cohort. The numerator will be the total number of participants with at least 1 PCS postbaseline value during

the specific period of the corresponding cohort. A supportive listing of participants with PCS postbaseline values will be provided for the safety population.

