#### **4.0 INTRODUCTION**

This statistical analysis plan (SAP) provides a more technical and detailed elaboration of the statistical analyses of the efficacy and safety data as outlined and/or specified in the amended version of the protocol of Study LIN-MD-67 (version 1.0, May 2020). Specifications of tables, figures, and data listings are contained in a separate document.

Study LIN-MD-67 is a Phase 2 randomized, double-blind, placebo-controlled, sequential, ascending multidose study with a 4-week Study Intervention Period in participants, 2 to 5 years of age, who meet Rome III criteria for childhood functional constipation (FC).

Up to 30 participants, 2 to 5 years of age, will be sequentially enrolled in up to four cohorts in LIN-MD-67 study; eight participants per cohort for Cohorts 1 to 3 and six participants in the final cohort. For each cohort, participants will be randomly assigned to receive linaclotide or matching placebo as described below. Up to 40 sites from the United States and Canada are expected to participate in the study.

The study will consist of up to 4 cohorts, each of which will be 9 to 12 weeks in duration: 2 to 4-week Screening Period, a 2 to 3-week Preintervention Period, followed by a 4-week double-blind Study Intervention Period, and a 1-week Postintervention Period. The raw datasets of study LIN-MD-67 capture Preintervention Period as Pretreatment Period, Study Intervention Period as Treatment Period, and Postintervention Period as Posttreatment Period.

Participants will not receive study intervention (i.e. study treatment) during the Screening/Preintervention Period and the Postintervention Period.

After at least 6 participants in Cohorts 1 to 3 complete at least 2 weeks of double-blind study intervention, an independent Data Safety and Monitoring Board (DSMB) will review unblinded interim safety data. Based on this review, the DSMB will recommend whether the subsequent planned dose level should be tested. New participants will be recruited for each cohort.

Refer to [Figure 4-1](#) for assignment of participants to dose cohorts.

- Cohorts 1-3: 8 participants will be randomized at a ratio of 3:1 to receive linaclotide or matching placebo:
  - Cohort 1: linaclotide 18 µg or matching placebo once daily for 4-week Study Intervention Period.

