## **11.0 SAFETY ANALYSES**

The safety analysis will be performed using the Safety Population. The safety parameters will include adverse events (AEs) and clinical laboratory parameters, vital sign (including postural), electrocardiographic (ECG) parameters, and weight. For each safety parameter of the clinical laboratory, vital signs, weight, and ECG parameters, the last non-missing safety assessment before the first dose of study intervention will be used as the baseline for all analyses of that safety parameter. Continuous variables will be summarized by number of participants and mean, SD, median, minimum, and maximum values. Categorical variables will be summarized by number and percentage of participants.

The safety summaries will be provided by study intervention group for each cohort separately. If any cohort has a similar linaclotide dose with another cohort, the safety summaries will also be provided combining participants from the similar dose cohorts. Summaries will also be provided for participants from all cohorts in the placebo group.

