### 11.3 VITAL SIGNS

Descriptive statistics for vital signs (ie, temperature, body weight, respiratory rate, supine pulse rate, supine systolic and diastolic blood pressure) and changes from baseline values at each assessment time point will be presented by study intervention group within the corresponding cohort.

Vital sign values will be considered PCS if they meet both the observed-value criteria and the change-from-baseline criteria listed in [Table 11.3–1](#). The number and percentage of participants with PCS postbaseline values will be tabulated by study intervention group within the corresponding cohort for the double-blind Intervention Period and Postintervention Period separately. The percentages will be calculated relative to the number of participants with available non-PCS baseline values and at least 1 postbaseline assessment in the specific period. The numerator will be the total number of participants with available non-PCS baseline values and at least 1 PCS postbaseline value during the specific period for the corresponding cohort. A supportive tabular display of participants with PCS postbaseline values will be provided, including the PID number, baseline and all postbaseline (including non-PCS) values.

In addition, a tabular display showing all AEs that occurred in participants who had PCS postbaseline vital sign values will be provided.

If any cohort has a similar linaclotide dose with another cohort, the above discussed vital signs summaries will also be provided combining participants from the similar dose cohorts. Summaries will also be provided for participants from all cohorts in the placebo group.

Table 11.3-1 Criteria for Potentially Clinically Significant Vital Signs

Parameter	Flag	Criteria a	
		Observed Value	Change From Baseline
Systolic Blood Pressure, mmHg - Postural Vital Signs (Supine and Standing)		Decrease in systolic blood pressure of 20 mmHg or more from supine to standing [*Change from supine SBP <= -20]	Decrease in systolic blood pressure from supine to standing at observed time point is at least 10 mmHg greater than the decrease in systolic blood pressure from supine to standing at baseline [Postbaseline change from supine SBP – baseline change from supine SBP <= -10]

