Diastolic Blood Pressure, mmHg Postural Vital Signs (Supine and Standing)		Decrease in diastolic blood pressure of 10 mmHg or more from supine to standing [Change from supine DBP <= -10]	Decrease in diastolic blood pressure from supine to standing at observed time point is at least 10 mmHg greater than the decrease in diastolic blood pressure from supine to standing at baseline [Postbaseline change from supine DBP – baseline change from supine DBP <= -10]
Pulse Rate, bpm - Postural Vital Signs (Supine and Standing)		Increase in heart rate of 20 beats per minute or more from supine to standing [Change from supine pulse rate >= 20]	Increase in heart rate from supine to standing at observed time point is at least 10 beats per minute greater than the increase in heart rate from supine to standing at baseline [Postbaseline change from supine pulse rate – baseline change from supine pulse rate >= 10]
Systolic Blood Pressure, mm Hg (Supine)	High	Age 2-5 (inclusive): $\geq 125$	Increase of $\geq 20$
	Low	Age 2-5 (inclusive): $\leq 70$	Decrease of $\geq 20$
Diastolic Blood Pressure, mm Hg (Supine)	High	Age 2-5 (inclusive): $\geq 85$	Increase of $\geq 15$
	Low	Age 2-5 (inclusive): $\leq 35$	Decrease of $\geq 15$
Pulse Rate, bpm (Supine)	High	Age 2-3, boy (inclusive): $\geq 165$ Age 4-5, boy (inclusive): $\geq 133$ Age 2-3, girl (inclusive): $\geq 188$ Age 4-5, girl (inclusive): $\geq 134$	Increase of $\geq 15$
	Low	Age 2-3, boy (inclusive): $\leq 87$ Age 4-5, boy (inclusive): $\leq 63$ Age 2-3, girl (inclusive): $\leq 85$ Age 4-5, girl (inclusive): $\leq 68$	Decrease of $\geq 15$
Weight, kg	High	—	Increase of $\geq 5\%$
	Low	—	Decrease of $\geq 5\%$

a A postbaseline value is considered potentially clinically significant if it meets both the observed-value and the change-from-baseline criteria.

bpm = beats per minute; DBP = diastolic blood pressure; SBP = systolic blood pressure.

\* Change from supine value = standing value – supine value

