**16.4 REPEATED OR UNSCHEDULED ASSESSMENTS OF SAFETY PARAMETERS**

If a participant has repeated assessments before the start of the first study intervention, the results from the final non-missing assessment made prior to the start of the study intervention will be used as baseline as appropriate unless specified. If end-of-study assessments are repeated or if unscheduled visits occur, the last non-missing postbaseline assessment will be used as the end-of-study assessment for generating summary statistics. However, all postbaseline assessments will be used for PCS value determinations, and all assessments will be presented in the data listings.

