**17.0            CHANGES TO ANALYSES SPECIFIED IN PROTOCOL**

There are no changes to analyses specified in the amended protocol (version 1.0, May 2020).

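### SAP 11.3 leaves out the standing blood pressure and pulse summaries planned in protocol 9.4.2.3 and declares no change; protocol Appendix 8 also describes postural readings as supine

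*SAP*

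**What the plan says.** **Analysis.** Protocol Section 9.4.2.3 plans "Descriptive statistics for weight and postural vital signs (supine and standing systolic and diastolic BP and pulse rate), respiration rate, and temperature", at baseline and as change from baseline at each time point. SAP Section 11.3 covers the same ground with "Descriptive statistics for vital signs (ie, temperature, body weight, respiratory rate, supine pulse rate, supine systolic and diastolic blood pressure". Its list is introduced by *ie*, so it reads as complete, and it contains no standing measurement.

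Two other SAP sections bear on this. Section 11.0 names among the safety parameters "clinical laboratory parameters, vital sign (including postural), electrocardiographic (ECG) parameters, and weight". Section 17.0 states: "There are no changes to analyses specified in the amended protocol (version 1.0, May 2020".

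Standing values do appear elsewhere in the SAP. Table 11.3-1 has three postural PCS criteria (systolic, diastolic, pulse), each based on standing minus supine and each compared with the same difference at baseline. The pulse criterion, for example, requires that the rise on standing "is at least 10 beats per minute greater than the increase in heart rate from supine to standing at baseline". Section 16.4 adds that "all postbaseline assessments will be used for PCS value determinations, and all assessments will be presented in the data listings".

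**Data collection.** Protocol Section 8.2.2, the vital-signs footnote to the protocol's Schedule of Activities, and footnote k to SAP Table 4-1 all define postural vital signs as supine and standing, taken in that order at all visits. Protocol Appendix 8 (Sections 10.8.1 to 10.8.6) describes them at each of the six visits as supine pressures and pulse, while citing Section 8.2.2.

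**The concern.** A programmer working from SAP 11.3 alone would produce no standing rows in the descriptive tables, and nothing in Section 17.0 would tell a reader that a protocol-planned safety summary had been dropped.

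The PCS table is not a substitute. A systolic flag needs both a supine-to-standing fall of at least 20 mmHg and a fall at least 10 mmHg larger than at baseline. Suppose, purely for illustration, that every child in a group moved from a 2 mmHg fall at baseline to an 18 mmHg fall on treatment, with supine pressure unchanged. The change is 16 mmHg, but 18 is below 20, so no systolic flag would be raised and the supine rows would show nothing. The shift would be visible only child by child in the listings. Events of special interest here include significant volume depletion related to diarrhea (protocol Section 8.3.1), so this is a signal the trial should be able to see at group level.

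The Appendix 8 wording raises a collection question: a site that read it literally would not obtain the standing readings that both the protocol summary and the postural PCS criteria need.

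**Working it through.** The plan gives no figure to reproduce on this point. The check is a comparison of lists, then arithmetic on denominators.

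**1. Parameters planned**

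| Parameter | Protocol 9.4.2.3 | SAP 11.3 |
|---|---|---|
| Weight | yes | yes |
| Temperature | yes | yes |
| Respiratory rate | yes | yes |
| Supine systolic BP | yes | yes |
| Supine diastolic BP | yes | yes |
| Supine pulse | yes | yes |
| Standing systolic BP | yes | **no** |
| Standing diastolic BP | yes | **no** |
| Standing pulse | yes | **no** |
| **Total** | **9** | **6** |

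9 − 6 = 3, all of them standing. The SAP list adds nothing that the protocol lacks.

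**2. Appendix 8 against Section 8.2.2.** Sections 10.8.1, 10.8.2, 10.8.3, 10.8.4, 10.8.5 and 10.8.6 all carry the supine wording: 6 of 6 entries.

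**3. What it would take to lose a postural baseline.** SAP 11.0 uses the last non-missing value before the first dose. The Schedule of Activities has vital signs at Visits 1, 2 and 3, and Section 10.8.3 gives the first dose after the Visit 3 assessments. There are therefore three scheduled pre-dose pairs, and all three would have to be missing.

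**4. Effect if one child had no postural baseline.** The SAP 11.3 PCS denominator is the "number of participants with available non-PCS baseline values and at least 1 postbaseline assessment in the specific period". Arm sizes at the planned maximum of 30 (SAP 14.0):

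- Cohorts 1 to 3: 8 × 3/4 = 6 active and 8 × 1/4 = 2 placebo in each.
- Final cohort: 6 × 5/6 = 5 active and 6 × 1/6 = 1 placebo.
- Pooled placebo: 2 + 2 + 2 + 1 = 7.
- Active, final cohort pooled with one earlier cohort at the same dose: 6 + 5 = 11.

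| Summary | Denominator | After losing one child |
|---|---|---|
| Placebo, Cohort 1, 2 or 3 | 2 | 1 |
| Placebo, final cohort | 1 | 0 |
| Placebo, pooled | 7 | 6 |
| Active, Cohort 1, 2 or 3 | 6 | 5 |
| Active, final cohort | 5 | 4 |
| Active, two cohorts pooled | 11 | 10 |

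These are conditional figures, not forecasts. They assume full enrollment, every other child evaluable and, for the 11, exactly one earlier cohort at that dose.

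**5. A second route.** The Postintervention Period is tabulated separately and has one scheduled visit, Visit 6. A supine-only reading there would remove a child from that period's postural PCS denominator even with an intact baseline, unless an unscheduled pair existed.

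**The case against.** - **Postural data are still analyzed.** True. The three postural PCS criteria are tabulated by group, by period and in the pooled summaries; all assessments are listed; and flagged children have all their values displayed. This confines the gap to the descriptive and change-from-baseline summary.
- **SAP 11.0 may already cover it.** Section 11.0 says that continuous safety variables will be summarized, and it includes postural vital signs, so it could be read as reaching the standing values. That softens the charge that the SAP contradicts itself. It does not remove the conflict between the specific list in 11.3 and protocol 9.4.2.3, or explain why 17.0 is silent.
- **The table specifications may include the rows.** SAP 4.0 says: "Specifications of tables, figures, and data listings are contained in a separate document". They may, so a missing output cannot be asserted. The text of the SAP is still wrong as it stands.
- **The summary adds little.** The protocol plans standing values, not the supine-to-standing difference; a mean over one or two placebo children is weak evidence; no test or decision rule uses it; and events of special interest rest on investigator or sponsor judgment. All fair. But where the same children contribute to both rows, the mean difference follows by subtraction, and in a trial analyzed descriptively such group summaries are the planned evidence.
- **Appendix 8 is an editorial slip.** Largely so. Each entry calls the readings postural and cites Section 8.2.2, and protocol Section 8 requires adherence to the Schedule of Activities. The risk of lost baseline data is limited, and nothing in the documents suggests it is likely.

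**Conclusion.** The concern holds. SAP 11.3 lists 6 of the 9 vital-sign parameters that protocol 9.4.2.3 plans to summarize, omits standing systolic pressure, diastolic pressure and pulse, and does so without a declared change in 17.0. Confidence is high for the mismatch in the text. Whether the output would actually be missing depends on table specifications that are not available.

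All 6 Appendix 8 visit entries conflict in wording with Section 8.2.2 and the Schedule of Activities footnote. Baseline data would be lost only if a site consistently followed the supine wording across all three pre-dose visits. A single supine-only reading at Visit 6 could affect the postintervention postural tabulation.

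This is a minor consistency correction that should be made. It does not remove postural data from the safety analysis, and it does not touch sample size, power or alpha.

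**What to change.** 1. In SAP 11.3, add standing systolic pressure, standing diastolic pressure and standing pulse to the descriptive and change-from-baseline tables, taking the list from 6 to 9. Alternatively, state and justify the omission in SAP 17.0.
2. Check that the separate table specifications agree with whichever is chosen.
3. Reconcile the wording of protocol Sections 10.8.1 to 10.8.6 with Section 8.2.2 and the Schedule of Activities footnote.

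The cost is rows for three parameters in existing tables, or one sentence in SAP 17.0, plus a wording correction at the next protocol update. No new procedure is needed, because Section 8.2.2 and the Schedule of Activities footnote already call for both positions.

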## 11.4 ELECTROCARDIOGRAM

Descriptive statistics for ECG parameters (ventricular heart rate, RR interval, PR interval, QRS interval, QT interval, and QTc) and changes from baseline values at each assessment time point will be presented by study intervention group within each cohort. The QTc will be calculated using both the Bazett and Fridericia corrections.

Electrocardiographic parameter values are considered PCS if they meet or exceed the higher-limit PCS criteria listed in [Table 11.4-1](#). The number and percentage of participants with PCS postbaseline ECG values will be tabulated by study intervention group for the double-blind intervention period within the corresponding cohort. The percentages will be calculated relative to the number of participants with available non-PCS baseline values and at least 1 postbaseline assessment for the double-blind Intervention Period within the corresponding cohort. The numerator is the total number of participants with available non-PCS baseline values and at least 1 PCS postbaseline value for the double-blind Intervention Period of the corresponding cohort. A supportive tabular display of participants with PCS postbaseline values will be provided, including the PID number, baseline, all postbaseline (including non-PCS) values, and change from baseline. In this listing, any participant with PCS value (if any) during Postintervention Period will also be included.

In addition, a tabular display showing all AEs that occurred in participants who had postbaseline PCS ECG values will be provided.

A shift table from baseline to the end of double-blind Intervention Period in the Investigator's overall interpretation of the ECG will be presented by study intervention group within each cohort for the following categories: normal; abnormal, not clinically significant; abnormal, clinically significant. A tabular display showing participants with postbaseline clinically significant ECG abnormalities according to the Investigator's overall interpretation will be provided.

If any cohort has a similar linaclotide dose with another cohort, the ECG summaries discussed above will also be provided combining participants from the similar dose cohorts and summaries will also be provided for participants from all cohorts in the placebo group.

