8.3.1. Adverse Events of Special Interest (AESIs)

AESIs are defined as significant volume depletion and/or significant electrolyte abnormalities and/or ECG abnormalities that are considered by the investigator or sponsor to be related to diarrhea. The investigator should contact the sponsor if there is any question whether the criterion for an AESIs has been met. All AESIs must be reported to the sponsor as described in Section 10.3.

8.3.2. Time Period and Frequency for Collecting Adverse Events, Serious Adverse Events, and Adverse Events of Special Interest Information

At each visit, participants are to be queried regarding any AEs or SAEs that have occurred since the previous visit. Participants will be asked to volunteer information with a nonleading question such as, "How do you feel since your last visit?" Study site personnel will record all pertinent information in the participant's eCRF. All SAE from the signing of the ICF until 30 days after the last dose of study intervention will be collected at the timepoints specified in the SoA (Section 1.3), and as observed or reported spontaneously by study participants.

All AEs from the signing of the ICF until 30 days after the last dose of study intervention will be collected at the timepoints specified in the SoA (Section 1.3), and as observed or reported spontaneously by study participants.

Medical occurrences that begin before the start of study intervention, but after obtaining informed consent will be recorded in the AE section of the eCRF.

All SAEs and serious AESIs of special interest will be recorded and reported to the sponsor or designee within 24 hours on an SAE form, as indicated in Section 10.3. Non-serious AESIs do not require submission on an SAE form; rather, these events only need to be entered into the eCRF. The investigator will submit any updated SAE data to the sponsor within 24 hours of it being available.

Investigators are not obligated to actively seek AE or SAE information after conclusion of the study participation. However, if the investigator learns of any SAE including a death, at any time after a participant has been discharged from the study, and he/she considers the event to be reasonably related to the study intervention or study participation, the investigator must promptly notify the sponsor.

The method of recording, evaluating, and assessing causality of AEs and SAEs and the procedures for completing and transmitting SAE reports are provided in Section 10.3.

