**Table 11.4-1 Criteria for Potentially Clinically Significant Electrocardiograms**

Parameter	Unit	Higher Limit
QRS interval	msec	QRS $\geq 115$ msec (2-5 (inclusive) years)
PR interval	msec	PR $> 225$ msec (2-5 (inclusive) years)
QTc(F)	msec	$>480$

QTc(F) = QT Corrected by Fridericia's formula

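### The QTc flag in SAP Table 11.4-1 is an absolute QTcF limit only, so a large rise that ends at or below 480 msec is not counted, and no table counts children by size of QTc increase

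*SAP*

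**What the plan says.** SAP 11.4 sets the rule: "Electrocardiographic parameter values are considered PCS if they meet or exceed the higher-limit PCS criteria listed in" Table 11.4-1. That table has three rows: QRS at 115 msec or more, PR above 225 msec, and QTcF above 480 msec. All are absolute limits. The note to the table, "QTc(F) = QT Corrected by Fridericia's formula", confirms that the QTc row is Fridericia only. The same section says "The QTc will be calculated using both the Bazett and Fridericia corrections", so Bazett values will exist but have no limit. Protocol 9.4.2.4 leaves the ECG criteria to the SAP and adds none.

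Three outputs in SAP 11.4 depend on these limits:
- the PCS count;
- the participant listing that prints change from baseline;
- the display of AEs in children with a PCS ECG value.

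Other outputs do not depend on them:
- Descriptive statistics for ECG values "and changes from baseline values at each assessment time point will be presented by study intervention group within each cohort". SAP 11.0 adds: "Continuous variables will be summarized by number of participants and mean, SD, median, minimum, and maximum values".
- "A shift table from baseline to the end of double-blind Intervention Period in the Investigator's overall interpretation of the ECG will be presented", together with a participant display of abnormalities that the investigator judged clinically significant.
- Data listings of every assessment (SAP 16.4).

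For vital signs the SAP works differently: "Vital sign values will be considered PCS if they meet both the observed-value criteria and the change-from-baseline criteria listed in" Table 11.3-1. In that table the weight row has no observed-value limit, so a change of 5% decides alone.

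**The concern.** ECG change is part of what this trial watches for. Protocol 8.3.1 states: "AESIs are defined as significant volume depletion and/or significant electrolyte abnormalities and/or ECG abnormalities", where these are judged related to diarrhea. Protocol 8.2 commits to active monitoring for severe diarrhea with electrolyte or ECG abnormality, and Protocol 2.2.4 reports electrolyte disturbance in adults after marketing. The signal of interest is therefore a change on treatment.

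The numeric QTc flag ignores change. A child can have a large rise, finish at or below 480 msec, and appear in none of the three outputs that depend on the limit. A reader of the PCS table could see zero QTc findings in a cohort where such a rise occurred. The one display that sets ECG values beside AEs would omit that child.

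**Working it through.** The plan states no figure to reproduce here: sample size has no statistical basis and there is no power statement. Two checks apply.

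**1. Which rises go uncounted**

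Input: QTcF > 480 msec (Table 11.4-1). A rise d from baseline b is not PCS when b + d ≤ 480, that is, when b ≤ 480 − d.

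| Rise d (msec) | Not counted if baseline is at or below |
|---|---|
| 60 | 480 − 60 = 420 |
| 90 | 480 − 90 = 390 |
| 120 | 480 − 120 = 360 |

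Examples: 400 to 460 is not PCS; 360 to 480 is not PCS; 380 to 500 is PCS; 421 to 481 is PCS. Above a baseline of 420, every rise of 60 or more is already flagged. The documents give no baseline QTcF, so the share of children in each range is unknown.

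**2. How the two rules behave**

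Assumptions, none from the documents: true rise 80 msec, single-ECG SD 15 msec, baseline 370 to 420 msec, and a proposed change cut-off of 60 msec.

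Current rule: P(flag) = 1 − Φ((480 − b − 80)/15).

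| Baseline b | (400 − b)/15 | P(flag) |
|---|---|---|
| 370 | 2.00 | 2% |
| 390 | 0.67 | 25% |
| 400 | 0 | 50% |
| 410 | −0.67 | 75% |
| 420 | −1.33 | 91% |

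Change rule: a difference of two ECGs has SD 15 × √2 = 21.2. P(change ≥ 60) = 1 − Φ((60 − 80)/21.2) = 83%, whatever the baseline. The two rules are equal near b = 400 + 15 × 0.943 = 414. For a true rise of exactly 60, the change rule flags 1 − Φ(0) = 50%.

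False flags in an unaffected child with one postbaseline ECG: 1 − Φ(60/(SD × √2)).

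| Assumed SD | 60/(SD × √2) | Per child | Expected in 30 children |
|---|---|---|---|
| 15 | 2.83 | 0.2% | 0.07 |
| 20 | 2.12 | 1.7% | 0.5 |
| 25 | 1.70 | 4.5% | 1.3 |

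Detection of a true 80 msec rise by the change rule falls to 1 − Φ(−20/28.3) = 76% at SD 20 and 1 − Φ(−20/35.4) = 71% at SD 25.

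**What the group summary shows.** At 3:1 in 8 children there are 6 on linaclotide. One child's rise of 60 to 120 msec moves the mean change by 60/6 = 10 to 120/6 = 20 msec, and the maximum shows the whole rise. However, SAP 16.1 takes the last non-missing value in each visit window, so an unscheduled ECG from Day 22 onward is superseded by a later end-of-treatment ECG. PCS determination uses all postbaseline assessments (SAP 16.4).

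**The case against.** A reader might infer that such a child would be reported as having no ECG abnormality. The documents do not support that. The maximum change by group would show the rise if it falls on the ECG used for that window. The investigator's shift table and the display of clinically significant abnormalities do not use the 480 limit. With at most 30 children and one scheduled ECG on each side of treatment, a reader could find the change in the full listings.

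Nor does AESI capture run through the PCS table. Readable ECGs go to cardiologist over-read (Protocol 8.2.3), the AESI is a judgement of the investigator or sponsor, and SAP 11.1 gives AESIs their own display and lists all AEs. These points stand. Their limit is that the judgement routes state no QTc rule, the group maximum names no child, and the listings flag nothing.

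A reader might also infer that the existing limit can hardly ever fire. That does not follow: under the same assumptions it flags 75% at baseline 410 and 91% at 420, and at 420 it does better than the change rule alone. Nothing in the documents says how extreme a QTcF of 480 is at ages 2 to 5.

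The vital-sign rule is not a model to copy. It requires both an observed value and a change; applied to QTcF it would flag no additional child. The closer precedent is the weight row, which flags on change alone.

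Finally, the 60 msec cut-off has no source in the documents, and the false-flag rate depends on an assumed SD for ECGs some 8 to 11 weeks apart (Screening 4 to 7 weeks before randomization, plus 4 weeks). Both objections are fair, so the cut-off is offered as a proposal and the rate as a range.

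**Conclusion.** The point holds as a reporting gap. QTcF above 480 msec is the only numeric QTc criterion, and no table counts children by size of QTc increase. A rise of 60, 90 or 120 msec from a baseline at or below 420, 390 or 360 respectively is missing from the PCS count, the PCS listing and the linked AE display. That follows directly from Table 11.4-1 and needs no assumption.

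The practical size depends on baseline QTcF and ECG variability, which the documents do not give. For an 80 msec rise at SD 15, detection under the current rule runs from 2% to 91% across assumed baselines of 370 to 420, against 83% for a change rule of 60 msec. The main gain is that detection no longer depends on where the child started. The current limit still helps at high baselines, so the change criterion should be added alongside it. This is an inexpensive improvement to a descriptive safety report. It does not show that ECG events would go undetected in the trial.

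**What to change.** In Table 11.4-1, keep QTcF above 480 msec and add a separate either/or category for QTcF increase from baseline, for example ≥ 60 msec. State that this is a reporting cut-off chosen for this analysis. Carry the category into the PCS table, the participant listing and the linked AE display, and apply it to all postbaseline ECGs, including unscheduled ones, as SAP 16.4 already provides for PCS determination. Define its denominator as children with a baseline and at least one postbaseline QTcF, since a non-PCS baseline has no meaning for a change. Do not require both criteria together.

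In the same edit, reconcile the text of SAP 11.4, which counts values that meet the limit, with the table, which uses strictly greater than for QTcF (480) and PR (225). A QTcF of exactly 480 is PCS by the text and not by the table. If the text governs, the uncounted baselines in the first check become strictly below 480 − d.

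The cost is one table row and its programming. The scheduled Screening and Week 4/EOT ECGs supply the data. Some false flags will occur at the rates shown above, with a little more opportunity where unscheduled ECGs are taken. The category affects reporting only and changes nothing in the management of participants.
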